6.1.2.9. Health-Related Quality of Life

The FACT-Leu questionnaire includes subscales for physical well-being (PWB, 7 items), social/family well-being (SWB, 7 items), emotional well-being (EWB, 6 items), functional well-being (FWB, 7 items), and additional concerns (Leukemia-Specific Subscale [LeuS], 17 items). The FACT-Leu scoring guide identifies those negatively stated items that must be reversed before being added to obtain subscale totals. Negatively stated items are reversed by subtracting the response from "4". After reversing proper items, all subscale items are summed to a total, which is the subscale score. For all FACT-Leu scales and symptom indices, the higher score is associated with the better quality of life. The scores in the following items need to be reversed according to the standard scoring guidelines:

- Physical well-being: all individual items
- Social/family well-being: none
- Emotional well-being: 5 individual items (except for GE2: "I am satisfied with how I am coping with my illness")
- Functional well-being: none
- Additional concerns: all individual items (except for C6: "I have a good appetite" and An7: "I am able to do my usual activities")

The subscale scores will be a summation of each individual item score. If $\leq 50\%$ of item scores are missing, the subscale score will be calculated by multiplying the sum of the item scores by the number of items in the subscale, then divided by the number of non-missing item scores. This imputes the missing scores by the mean of the non-missing scores within a subscale.

Prorated subscale score = [sum of item scores] × [N of items in subscale] / [N of items answered]

The following composite scores will be derived from the above subscale total scores:

- Trial Outcome Index (TOI, score range: 0-124) = PWB + FWB + LeuS
- FACT-G Total Score (score range: 0-108) = PWB + SWB + EWB + FWB
- FACT-Leu Total Score (score range: 0-176) = PWB + SWB + EWB + FWB + LeuS

The total scores will be set to missing if 20% or more of the included items are missing or any of the component subscales are missing. TOI scores are set to missing if any of the component subscales are missing.

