As a baseline, the last value obtained prior to the baseline reference date for efficacy endpoints, as defined in Section 3.5.1, will be used. The mean and change from baseline in mean scores to each subsequent assessment will be summarized for the subscale and composite scores. The best change from baseline during the study, defined as the highest positive value among all post-baseline visits minus the baseline value, will also be summarized.

Each subject's FACT-Leu subscales (ie, PWB, EWB, SWB, and FWB) scores at each assessment will be compared to their baseline scores. The minimally important difference (MID) for these subscales is 3 points {26297}. An increase of at least 3 points will be required as a definition of symptom improvement. The cumulative distribution function (CDF) of best change from baseline will be provided. For the MID improvement comparison, subjects with baseline score > 55 will be excluded (ie, subjects with no room for improvement). Time to symptom response will be assessed by defining the first occurrence of symptom improvement as an event. Subjects who do not experience a symptom improvement compared to baseline will be censored at their last available FACT-Leu assessment time.

A data listing for each individual item, the subscale scores, and the composite scores will be presented for each subject at each time point.

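### The FACT-Leu exclusion of baseline scores above 55 cannot be met on the four subscales it governs (maxima 28 or 24), so it removes nobody

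*SAP*

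**What the plan says.** SAP section 6.1.2.9 describes the FACT-Leu scoring and the responder analysis. Four of the subscales are "physical well-being (PWB, 7 items), social/family well-being (SWB, 7 items), emotional well-being (EWB, 6 items), functional well-being (FWB, 7 items"; the fifth is "additional concerns (Leukemia-Specific Subscale [LeuS], 17 items". Item scores are summed without rescaling. The general composite is given as "FACT-G Total Score (score range: 0-108) = PWB + SWB + EWB + FWB". Missing items are prorated: "This imputes the missing scores by the mean of the non-missing scores within a subscale".

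The improvement analysis is limited to four subscales: each subject's "FACT-Leu subscales (ie, PWB, EWB, SWB, and FWB) scores at each assessment will be compared to their baseline scores". The MID for these is set at 3 points, and "An increase of at least 3 points will be required as a definition of symptom improvement". The exclusion follows: "For the MID improvement comparison, subjects with baseline score > 55 will be excluded (ie, subjects with no room for improvement". The section then defines time to symptom response, with first improvement as the event: "Subjects who do not experience a symptom improvement compared to baseline will be censored at their last available FACT-Leu assessment time".

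**The concern.** The parenthesis in the exclusion sentence gives its purpose: to take out subjects who start too high to improve. A single cut-off of 55 cannot do that on scales that end at 24 or 28. If the filter is empty, the comparison runs on all subjects rather than on those able to improve.

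Subjects at the ceiling then count as failures by construction. The proportion improved is pulled down, and so is the share reaching symptom response, because these subjects can only be censored there. A programmer who notices the problem must either run an empty filter or pick another cut-off. SAP section 3.5.1 records that the primary study has been unblinded, so an undocumented choice could be made with the data in view.

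**Working it through.** **Inputs.** Item counts are from SAP 6.1.2.9: physical 7, social/family 7, emotional 6, functional 7, leukemia-specific 17. Items score 0 to 4: the SAP reverses negative items by subtracting from 4, and the form in protocol Appendix 2 shows responses 0 to 4. The MID is 3 points and the cut-off is 55.

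**Step 1: reproduce the SAP's ranges.** Maximum = 4 × number of items.
- Physical, social/family, functional: 4 × 7 = 28 each
- Emotional: 4 × 6 = 24
- Leukemia-specific: 4 × 17 = 68
- FACT-G: 28 + 28 + 24 + 28 = 108 (SAP: 108)
- Trial Outcome Index: 28 + 28 + 68 = 124 (SAP: 124)
- FACT-Leu total: 108 + 68 = 176 (SAP: 176)

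All three composite ranges agree, so the subscale maxima are the SAP's own.

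**Step 2: can proration exceed a maximum?** With a of N items answered, the largest prorated score is 4a × N / a = 4N. With 4 of 7 answered: 16 × 7/4 = 28. With 3 of 6 answered: 12 × 6/3 = 24. It cannot.

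**Step 3: apply the cut-off.** 55 is above both 28 and 24, so no baseline on the four named subscales exceeds it. The number excluded is 0.

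**Step 4: who cannot improve?** A 3-point gain is impossible when baseline > maximum − 3.
- Physical, social/family, functional: 28 − 3 = 25, so whole-number baselines of 26 to 28
- Emotional: 24 − 3 = 21, so whole-number baselines of 22 to 24

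**Step 5: does 55 fit another score?**
- Leukemia-specific (maximum 68): a baseline of 56 leaves 12 points, and with a 3-point MID baselines of 56 to 65 could still improve.
- FACT-G: 108 − 56 = 52 points left
- Trial Outcome Index: 124 − 56 = 68 points left
- FACT-Leu total: 176 − 56 = 120 points left

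With a 3-point MID, 55 would suit a scale with maximum 55 + 3 = 58. The SAP has no such scale.

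**Step 6: size of the effect.** Let c be the share starting too high to gain 3 points, and p the improvement rate among the rest. With the empty filter, the reported rate is p × (1 − c). The documents give no baseline FACT-Leu distribution, so c is an assumption, shown from 0 to 40%.

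| p | c = 0 | 5% | 10% | 20% | 40% |
|---|---|---|---|---|---|
| 30% | 30% | 28.5% | 27% | 24% | 18% |
| 50% | 50% | 47.5% | 45% | 40% | 30% |
| 70% | 70% | 66.5% | 63% | 56% | 42% |

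**The case against.** The arithmetic is not in dispute; the case against is about weight.

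- **Reach.** SAP section 3.5.2 makes the analyses descriptive with no formal comparison between groups. Appendix 1 lists FACT-Leu outputs for change from baseline and for the cumulative distribution of best change, but none for MID improvement or time to symptom response. The listed outputs do not depend on the cut-off, and subject-level scores are listed, so a corrected rule could be applied later. This stands and limits the importance of the point.
- **The statistic.** The SAP does not spell out a proportion improved or its denominator. That reading is inferred from the decision to exclude subjects from an improvement comparison. It is the natural reading, but it is a reading.
- **Size.** Nothing in the documents supports a large ceiling share. Protocol section 3.2.2.2 describes impaired well-being in CLL, which points away from the upper end. The table is illustrative only.
- **Time to symptom response.** The exclusion is attached only to the MID comparison, so keeping ceiling subjects as censored there follows the text. This is an ambiguity rather than a breach of a stated rule.
- **Other readings.** The SAP assigns no MID to the leukemia-specific subscale, so the 3-point calculation for it is conditional. If a composite was meant, the rule would remove subjects with ample headroom; the consequence would differ, but the rule would still contradict its stated purpose.
- **Remedy.** Deleting the sentence and analysing everyone would also remove the contradiction.

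None of this makes the cut-off work.

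**Conclusion.** The concern holds. On the SAP's own item counts and scoring, the exclusion is empty for all four subscales it governs, and no other score in the section makes 55 a ceiling. This part is certain and needs no outside source.

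The consequence is either none or dilution: the reported proportion improved falls by the factor 1 − c. That rests on the literal subscale reading and on an unknown c. The share reaching symptom response is lowered in the same direction if ceiling subjects are kept in that analysis. Mean change and the cumulative distribution of best change are unaffected. This is an error that should be corrected in a descriptive quality-of-life analysis; it does not threaten the main findings.

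**What to change.** In SAP section 6.1.2.9, replace the single cut-off with each subscale's maximum minus 3: exclude baseline scores above 25 for physical, social/family and functional well-being, and above 21 for emotional well-being. State whether the same exclusion applies to time to symptom response; applying it there too would keep the two analyses consistent. If 55 was meant for another score, name that score and use its own maximum minus its own MID. Say also whether the leukemia-specific subscale is meant to be covered, since Appendix 1 plans a distribution figure for it.

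The cost is one or two sentences and a somewhat smaller denominator that differs by subscale. Nothing in trial conduct changes. If differing denominators are unwanted, the alternative is to delete the exclusion and say that all subjects are included, accepting the dilution. Either change should be made before these analyses are run; the documents do not show whether that has already happened.

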6.1.2.10. Karnofsky Performance Status

The Karnofsky performance status scores and the change from baseline scores to each subsequent assessment will be summarized. The best change from baseline, defined as the highest change from baseline during the study, will also be summarized.

6.1.2.11. EQ-5D

The EQ-5D questionnaire data will be scored, processed, and standardized according to the user manual. As for the FACT-Leu, data will be analyzed using appropriate methods specified in the user manual to account for incomplete completion of questionnaires. A single utility index of EQ-5D will be derived by applying US preference-weighted index {28010}. Data collected from the EQ-5D will not be reconciled with adverse event or laboratory data or with FACT-Leu findings.

Each EQ-5D dimension will be summarized using frequency and proportion. Change from baseline in EQ-5D visual analogue scale (VAS) and EQ-5D index will be summarized.

6.1.3. Between-Study Comparisons

6.2. Changes From Protocol-Specified Efficacy Analyses

The per-protocol analysis set and the safety analysis set are no longer applicable. The FAS will be used for both efficacy and safety analyses.

7. SAFETY ANALYSES

7.1. Adverse Events and Deaths

The focus of adverse event (AE) summarization will be on treatment-emergent AEs (TEAEs). All AEs and deaths happened on study will be summarized by treatment group and will be listed in detail based on the FAS.

7.1.1. Adverse Event Dictionary

AEs will be coded using the Medical Dictionary for Regulatory Activities (MedDRA) by system organ class (SOC), high level group term (HLGT), high level term (HLT), preferred term (PT), and lower level term (LLT).

7.1.2. Adverse Event Severity

The severity of AEs will be graded by the investigator according to the common terminology criteria for adverse events (CTCAE), Version 4.03, whenever possible. If a CTCAE criterion does not exist, the grade corresponding to the appropriate adjective will be used by the investigator to describe the maximum intensity of the AE. The severity grade will be categorized as:

- Grade 1 (mild)
- Grade 2 (moderate)
- Grade 3 (severe)
- Grade 4 (life threatening), or
- Grade 5 (fatal)

A missing severity grade will be considered as missing.

7.1.3. Relationship of Adverse Events to Study Drug

The relationship of an AE to IDELA should be assessed using clinical judgment by the investigator, describing the event as either unrelated or related. Events for which the investigator did not record relationship to IDELA will be considered related to IDELA. Data listings will show relationship as missing.

7.1.4. Serious Adverse Events

Serious adverse events (SAEs) are those identified as serious in the clinical database. The clinical database will be reconciled with the SAE database from the Drug Safety and Public Health (DSPH) Department before database finalization.

7.1.5. Treatment-Emergent Adverse Events

7.1.5.1. Definition of Treatment-Emergent

TEAEs are events in a given study period that meet one of the following criteria:

- Events with onset dates on or after the start of IDELA and up to 30 days after the permanent discontinuation of IDELA.
- AEs resulting in IDELA discontinuation after the start of treatment.

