8.5. Grading of the Severity of an Adverse Event

The severity of adverse events will be graded using the CTCAE, Version 4.03 (provided in study manual and available at

http://evs.nci.nih.gov/ftp1/CTCAE/CTCAE_4.03_2010-06-14_QuickReference_8.5x11.pdf). For each episode, the highest severity grade attained should be reported.

If a CTCAE criterion does not exist, the investigator should use the grade or adjectives: Grade 1 (mild), Grade 2 (moderate), Grade 3 (severe), Grade 4 (life-threatening), or Grade 5 (fatal) to describe the maximum intensity of the adverse event. For purposes of consistency with the CTCAE, these intensity grades are defined in Table 8-1.

Table 8-1. Grading of Adverse Event Severity

Grade	Adjective	Description	
Grade 1	Mild	Sign or symptom is present, but it is easily tolerated, is not expected to have a clinically significant effect on the subject's overall health and well-being, does not interfere with the subject's usual function, and is not likely to require medical attention.	
Grade 2	Moderate	Sign or symptom causes interference with usual activity or affect clinical status, and may require medical intervention.	
Grade 3	Severe	Sign or symptom is incapacitating or significantly affects clinical status and likely requires medical intervention and/or close follow-up.	
Grade 4	Life-threatening	Sign or symptom results in a potential threat to life.	
Grade 5	Fatal	Sign or symptom results in death.	

The distinction between the seriousness and the severity of an adverse event should be noted. Severe is a measure of intensity; thus, a severe reaction is not necessarily a serious reaction. For example, a headache may be severe in intensity, but would not be classified as serious unless it met one of the criteria for serious events listed in Section 8.1.2 above.

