9.4.3.4. Adverse Events

All adverse events will be listed. The focus of adverse event summarization will be on treatment-emergent adverse events. A treatment-emergent adverse event is defined as an adverse event that occurs or worsens in the period from the first dose of study treatment to 30 days after the last dose of study treatment.

Adverse events will be classified using MedDRA (http://www.meddramsso.com) with descriptions by System Organ Class, High-Level Group Term, High-Level Term, Preferred Term, and Lower-Level Term. The severity of adverse events will be graded by the investigator according to the CTCAE, Version 4.03 (http://evs.nci.nih.gov/ftp1/CTCAE/CTCAE_4.03_2010-06-14_QuickReference_8.5x11.pdf), whenever possible. If a CTCAE criterion does not exist for a specific type of adverse event, the grade corresponding to the appropriate adjective will be used by the investigator to describe the maximum intensity of the adverse event: Grade 1 (mild), Grade 2 (moderate), Grade 3 (severe), Grade 4 (life threatening), or Grade 5 (fatal). The relationship of the adverse event to the study drug will be categorized as related or unrelated.

Treatment-emergent adverse events will be summarized by treatment arm and by visit. Summary tables will be presented to show the number of subjects reporting treatment-emergent adverse events by severity grade and corresponding percentages. A subject who reports multiple treatment-emergent adverse events within the same Preferred Term (or System Organ Class) is counted only once for that Preferred Term (or System Organ Class) using the worst severity grade. Adverse event descriptions will be presented by decreasing frequency for a given System Organ Class and Preferred Term.

Separate listings and summaries will be prepared for the following types of treatment-emergent adverse events:

- Study-drug-related adverse events
- Adverse events that are Grade ≥3 in severity
- Adverse events leading to study drug interruption and/or dose modification
- Adverse events leading to study drug discontinuation
- Serious adverse events (with categorization of the primary reason that the adverse event is considered serious, eg, death, hospitalization, etc)

Separate listings and summaries will be prepared for long-term follow-up safety data (see Section 6.2.17).

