 - Baseline for efficacy and safety endpoints will be the first dosing of IDELA, unless otherwise specified.
 - In the analysis, the Study GS-US-312-0117 portion will include all the data collected on or after the first dosing date of IDELA. The Study GS-US-312-0117 portion may include data collected in Study GS-US-312-0116, if a subject switches to open-label IDELA in Study GS-US-312-0116 while waiting for the protocol amendment.
- Placebo in GS-US-312-0116 + IDELA 150 mg BID in GS-US-312-0117:
 - Includes subjects who experience IRC confirmed PD in Arm B of Study GS-US-312-0116 and subsequently enroll into Study GS-US-312-0117 to receive IDELA 150 mg BID during the double-blind portion of the study
 - Referred to 'Placebo+R (PD)/IDELA' throughout this SAP and the TFLs
 - Baseline for efficacy and safety endpoints will be the first dosing of IDELA, unless otherwise specified.
 - In the analysis, the Study GS-US-312-0117 portion will include all the data collected on or after the enrollment date of Study GS-US-312-0117.

Efficacy and safety data collected during the primary and extension studies will be presented in the following 3 treatment groups:

- IDELA+R (PD, non-PD)/IDELA
 - Includes all subjects who are randomized to Arm A in Study GS-US-312-0116 (ie, all subjects in IDELA+R/IDELA and IDELA+R (PD)/IDELA)
 - For those in IDELA+R (PD)/IDELA, only data collected in Study GS-US-312-0116 (ie, while taking IDELA 150 mg BID) will be included. For those in IDELA+R/IDELA, all the data collected across Study GS-US-312-0116 and GS-US-312-0117 will be included. By this summary, the efficacy and safety profile of IDELA 150 mg BID can be explored for subjects randomized to Arm A in Study GS-US-312-0116.

- Baseline for efficacy endpoints will be the date of randomization in Study GS-US-312-0116.
- Baseline for safety endpoints will be the first dosing of IDELA 150 mg BID in Study GS-US-312-0116.
- Placebo+R/IDELA
- Placebo+R (PD)/IDELA

Due to the small sample size (N = 4) for the IDELA + R (PD)/IDELA group, data collected from this group in Study GS-US-312-0117 (ie, while taking IDELA 300 mg BID) will only be presented in listings.

Baseline for each data summary is described in Table 3-1.

	Baseline for Disposition Summary		Baseline for Efficacy Summary		Baseline for Safety Summary
Treatment Group	312-0116	312-0117	All endpoints except for OS	OS	All endpoints

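### The SAP omits worsening from its treatment-emergent definition without declaring it, so some adverse events that begin before idelalisib and worsen on it can miss the TEAE tables

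*SAP*

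**What the plan says.** Protocol 9.4.3.4 defines a TEAE as "an adverse event that occurs or worsens in the period from the first dose of study treatment", with the window closing 30 days after the last dose.

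SAP 7.1.5.1 opens with "TEAEs are events in a given study period that meet one of the following criteria" and gives two:

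- The first goes by date: "Events with onset dates on or after the start of IDELA", in a window that closes 30 days after the drug is stopped for good.
- The second goes by outcome and sets no condition on the onset date: "AEs resulting in IDELA discontinuation after the start of treatment".

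Neither mentions worsening. SAP 7.6, the section for departures from the protocol's safety analyses, lists only the removal of the compliance summary. For laboratory abnormalities, SAP 7.2.3.1 keeps a worsening criterion of at least one grade from baseline.

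On recording, Protocol 8.5 says "For each episode, the highest severity grade attained should be reported". Protocol 8.1.1 treats a pre-existing condition that becomes more severe as an adverse event. Neither document says whether that worsening gets a separate record with a new onset date.

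SAP 3.5.1 and Table 3-1 set the safety baseline for both Arm B groups at the first idelalisib dose. For the Placebo+R/IDELA group, the extension-study data may include data collected in Study 0116 "if a subject switches to open-label IDELA in Study GS-US-312-0116 while waiting for the protocol amendment". Protocol 5.1.2 also lets placebo subjects enrol in Study 0117 and start idelalisib later, at the investigator's discretion.

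**The concern.** The SAP is narrower than the protocol on a basic safety definition, and the difference is not declared. It removes events in one direction only: those already present at the first idelalisib dose that get worse on the drug.

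This matters most in the Arm B groups. Their subjects have a period on placebo plus rituximab before idelalisib, so they can have events ongoing at first dose. Arm A's 150 mg safety data are anchored at the first idelalisib dose in Study 0116, so no placebo period comes before it. Groups shown side by side would be affected differently. Describing the safety profile of idelalisib is a stated objective, and in a descriptive study the adverse event tables are a main output.

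**Working it through.** The point concerns a definition, so the plan has no figure to reproduce. The check applies each rule to the same test events.

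**Set-up (illustrative days).** First idelalisib dose on day 1, last dose on day 200, window end 200 + 30 = day 230.

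- Protocol rule: onset in days 1 to 230, or worsening in days 1 to 230.
- SAP rule: onset in days 1 to 230, or the event leads to idelalisib discontinuation.

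| Case | Onset | Worsens | Leads to discontinuation | Protocol | SAP |
|---|---|---|---|---|---|
| A. New event on idelalisib | day 40 | – | no | TEAE | TEAE |
| B. Begins before idelalisib, reaches Grade 3 or higher on it | day −20 | day 40 | no | TEAE | **not TEAE** |
| C. As B, but idelalisib is stopped for it | day −20 | day 40 | yes | TEAE | TEAE |
| D. As B, but the worsening is a new record | day 40 | – | no | TEAE | TEAE |
| E. Begins before idelalisib, never worsens | day −20 | – | no | not TEAE | not TEAE |

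The rules differ only in case B. They differ there even if the event is serious or causes an interruption or dose reduction, because the SAP's second criterion covers discontinuation alone.

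**Outputs affected.** SAP 7.1.6 builds its Grade 3 or higher, serious, interruption, reduction and fatal-event summaries on TEAEs. SAP 7.1.7 (events of interest) and 7.1.8 (exposure-adjusted rates) also use TEAEs. A case B event is absent from each of these that it would otherwise enter.

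**Who can produce case B.**

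1. Subjects who switched to open-label idelalisib inside Study 0116 (SAP 3.5.1). They cross no study boundary at the first dose, so an ongoing episode can stay on one record with its placebo-period onset date.
2. Placebo subjects who delayed idelalisib after joining Study 0117 (Protocol 5.1.2). Protocol 8.6 starts adverse event reporting at 0117 consent, so an event can begin in 0117 before the first dose and peak after it.

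**Size.** The share of subjects affected is the proportion with an event ongoing at first dose, times the proportion of those who worsen on drug, times the proportion whose worsening neither leads to discontinuation nor is entered as a new record. The documents give none of the three, so no percentage is offered.

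**The case against.** A reader might infer that every event that worsens on idelalisib after an earlier onset disappears from all TEAE tables. The documents do not support that.

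- The second SAP criterion admits any event that leads to idelalisib discontinuation, whatever its onset date. This stands.
- For subjects whose first dose follows 0117 consent, Protocol 8.1.1 sends conditions with onset before consent to medical history and counts later worsening as an adverse event, and Protocol 8.6 assigns new events after consent to Study 0117. It is plausible that many carried-over events that worsen are entered as new 0117 records, which the first criterion captures. This largely stands, and it narrows the gap to the two routes above. It does not close the gap, because the entry conventions are left to a CRF completion guideline that is not part of these documents.
- Protocol 8.5 keeps only the highest grade per episode, so restoring the missing words alone would not show whether the peak came before or after the first dose. This stands, and the fix must deal with it.
- Excluded events remain visible in Listings 3.4.1 (all adverse events) and 3.4.9 (non-treatment-emergent events), deaths appear in Table 3.1.26, and worsening liver and blood values are caught by the laboratory tables. This is true, but listings do not correct incidence tables, and laboratory tables do not cover clinical events such as diarrhea or rash.
- Different rules for laboratory data and adverse events are not in themselves a fault, since laboratory values are graded at each visit and adverse events by episode. This stands. The laboratory rule shows only that the SAP did not abandon worsening in general.

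**Conclusion.** The point holds in a limited form. The SAP leaves out a limb of the protocol's definition and does not say so. As written, it excludes an event with onset before the first idelalisib dose that worsens on idelalisib, unless the event leads to discontinuation or the worsening has its own dated record. The exposed subjects are in the Arm B groups, chiefly through the two routes identified.

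The conclusion rests on one assumption: that for at least some of these subjects, worsening stays on the original record. The documents neither require nor rule this out.

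It would go too far to say that the safety profile is understated by a known amount, or that it certainly is understated. The number of affected events cannot be derived from the documents. What can be said is that any error from this source lowers the TEAE counts. The change is worth making because the departure is undeclared, works in one direction and is cheap to correct.

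**What to change.** 1. In SAP 7.1.5.1, restore the worsening limb: onset, or worsening in severity, on or after the first dose of idelalisib and up to 30 days after the last dose. Keep the discontinuation criterion.
2. Add a conservative rule for events ongoing at the first idelalisib dose, because only one highest grade is kept per episode. Count such an event as treatment-emergent at its maximum grade if either condition holds:
   - a dated record places the worsening on idelalisib (a serious adverse event report, an interruption or reduction due to the event, or a new adverse event entry);
   - the timing of the worsening relative to the first dose cannot be determined.
3. State in the SAP how grade increases in ongoing events are recorded and dated.
4. If the narrower definition is intended, declare and justify it in SAP 7.6 instead.

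The cost is a wording change and a small amount of programming with Study 0116 adverse event records for the Arm B groups. The undetermined-timing rule may over-count slightly, since it can admit an event that peaked before idelalisib. Reporting how many events enter by that route would show the extent.
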